7.4.2. Population of Interest

The immunogenicity analyses will be based on the Safety population, unless otherwise specified.

7.4.3. Statistical Analyses / Methods

Details of the planned displays are provided in [Appendix 12: List of Data Displays](#) and will be based on GSK Data Standards and statistical principles.

Unless otherwise specified, endpoints / variables defined in Section 7.4.1 will be summarised using descriptive statistics, graphically presented (where appropriate) and listed.

8. SAFETY ANALYSES

The safety analyses will be based on the Safety population, unless otherwise specified.

8.1. Adverse Events Analyses

The definition of an AE is detailed in Appendix 3 of the protocol. Any reported skin reactions will be recorded as Adverse Events as mentioned in the protocol.

Analyses of AEs will only include those events that are on-treatment as defined in [Appendix 4: Study Phases and Treatment Emergent Adverse Events \(Section 12.4\)](#).

Adverse events analyses including the analysis of adverse events (AEs), Serious (SAEs) and other significant AEs will be based on GSK Core Data Standards.

The details of the planned displays are provided in [Appendix 12: List of Data Displays](#).

8.2. Clinical Laboratory Analyses

Laboratory evaluations will be based on GSK Core Data Standards and will include:

- Haematology laboratory tests
- Chemistry laboratory tests
- Urinalysis
- Other screening tests

Clinical laboratory analyses will include all assessments post-baseline.

Details of the planned displays are presented in [Appendix 11: List of Data Displays](#)

The laboratory assessments for each category are displayed below (Table 2 of the protocol):

Laboratory Assessments	Parameters			
Haematology	Platelet Count	RBC Indices: MCV MCH %Reticulocytes	WBC count with Differential: Neutrophils Lymphocytes Monocytes Eosinophils Basophils	
	RBC Count			
	Haemoglobin			
	Haematocrit			
Clinical Chemistry ¹	BUN	Potassium	Aspartate Aminotransferase (AST)/ Serum Glutamic-Oxaloacetic Transaminase (SGOT)	Total and direct bilirubin

Laboratory Assessments	Parameters			
	Creatinine	Sodium	Alanine Aminotransferase (ALT)/ Serum Glutamic-Pyruvic Transaminase (SGPT)	Total Protein
	Glucose (non-fasting)	Calcium	Alkaline phosphatase	³ Complement protein C3 and C4
Routine Urinalysis ²	
 Specific gravity pH, glucose, protein, blood, ketones, bilirubin, urobilinogen, nitrite, leukocyte esterase by dipstick Microscopic examination (if blood or protein is abnormal) 			
Other Screening Tests	
 Breath alcohol test Urine drug screen (to include at minimum: amphetamines, barbiturates, cocaine, opiates, cannabinoids and benzodiazepines) HIV antibody, hepatitis B surface antigen [HBsAg], hepatitis B core antibody [HbcAb] and hepatitis C virus antibody) QuantiFERON test Urine albumin-creatinine ratio (UACR) 
The results of each test must be entered into the medical notes.
			
Other screening and follow up tests	
 Troponin-T (high sensitivity) NT-proBNP 			

NOTES:

- Details of liver chemistry stopping criteria and required actions and follow-up assessments after liver stopping or monitoring event are given in Section 7.1 and Appendix 5 of the protocol. All events of ALT $\geq 3 \times$ upper limit of normal (ULN) and bilirubin $\geq 2 \times$ ULN ($> 35\%$ direct bilirubin) or ALT $\geq 3 \times$ ULN and international normalized ratio (INR) > 1.5 , if INR measured, which may indicate severe liver injury (possible Hy's Law), must be reported as an SAE (excluding studies of hepatic impairment or cirrhosis).
- Local urine testing will be standard for the protocol unless serum testing is required by local regulation or IRB/IEC.
- Complement protein C3 and C4 to be performed (as baseline).

Laboratory/analyte results that could unblind the study will not be reported to investigative sites or other blinded personnel until the study has been unblinded.

8.3. Other Safety Analyses

The analyses of non-laboratory safety test results will be based on GSK Core Data Standards, unless otherwise specified.

The non-laboratory safety test results include:

- Vital Signs
- ECGs

The details of the planned displays are presented in [Appendix 12: List of Data Displays](#).

9. PHARMACOKINETIC ANALYSES

9.1. Drug Concentration Measures

Refer to [Appendix 5](#): Data Display Standards & Handling Conventions (Section 12.5.3 Reporting Standards for Pharmacokinetic).

9.2. Derived Pharmacokinetic Parameters

Pharmacokinetic parameters will be calculated by standard non-compartmental analysis according to current working practices and using the currently supported version of WinNonlin. All calculations will be based on actual sampling times.

Pharmacokinetic parameters listed below will be determined from the serum GSK3858279 concentration-time data, as data permits. Additional parameters may be included as required.

Parameter	Parameter Description
AUC(0-t)	
 Area under the concentration-time curve from time zero to the time of the last quantifiable concentration (C(t)) Calculated using the linear trapezoidal rule for each incremental trapezoid and the log trapezoidal rule for each decremental trapezoid.
AUC(0-7)	
 Area under the concentration-time curve from time zero (Day 1) to 7 days post-dose (Day 8) Calculated using the linear trapezoidal rule for each incremental trapezoid and the log trapezoidal rule for each decremental trapezoid
Cmax	
 Maximum observed concentration Determined directly from the concentration-time data.
tmax	
 Time to reach Cmax Determined directly from the concentration-time data
tlast	
 Time of occurrence of last quantifiable concentration Determined directly from the concentration-time data

NOTES:

Additional parameters may be included as required.

9.3. Population of Interest

The pharmacokinetic analyses will be based on the PK population, unless otherwise specified.

9.4. Statistical Analyses / Methods

Details of the planned displays are provided in [Appendix 12](#): List of Data Displays and will be based on GSK Data Standards and statistical principles.

Unless otherwise specified, endpoints / variables defined in Section 9.2 will be summarised using descriptive statistics by study period, graphically presented (where appropriate) and listed.

10. PHARMACOKINETIC / PHARMACODYNAMIC ANALYSES

The primary goal of this analysis is to characterize the pharmacokinetic / pharmacodynamic (PK/PD) relationship of GSK3858279 administered IV in healthy participants.

The PK and TE data may also be integrated with ongoing and planned studies to develop a Population PK/TE model for GSK3858279. Details of this integrated analysis will be described in a separate PDAP.

10.1. Statistical Analyses / Methods

A summary of the planned PK/PD analyses is outlined below:

- An exploratory graphical analysis will be performed to assess the relationship between observed measures of nociception and individual PK or TE data. If the exploratory graphical analysis suggests a relationship and data permits, direct or indirect response models may be developed and linked with the previous popPK/TE model to characterise the relationship between different modalities of nociception and PK or TE. Details of this analysis, if required, will be described in a separate SAP.
- To support this analysis, a PK/PD dataset will be generated. The details for the dataset specifications are provided in [Appendix 9: Pharmacokinetic / Pharmacodynamic Analyses](#).
- S&P will deliver 6 PK/PD figures, as detailed in Section [12.11.11: Pharmacokinetic / Pharmacodynamic Figures](#) as part of the AAC package.

12. APPENDICES

12.1. Appendix 1: Protocol Deviation Management and Definitions for Per Protocol Population

The full list of protocol deviations collected on the eCRF is in the Protocol Deviation Management Plan (PDMP). Please refer to this document for current guidance.

12.1.1. Exclusions from Per Protocol Population

There is no Per Protocol population in this study.

12.2. Appendix 2: Schedule of Activities

12.2.1. Protocol Defined Schedule of Events

12.2.1.1. Screening and Follow-Up

Procedure	Screening (up to 28 days before Day 1)		Follow-up check 36 ± 4 days post last dose	Final follow-up 56 ± 4 days post-last dose	Notes
	Part 1	Part 2			
Out-patient visit	X	X		X	Optional in-clinic stay for participants at the discretion of investigator.
Phone call			X		AE collection - may be out-patient visit at discretion of Investigator for additional checks
Informed consent	X				
Severe acute respiratory syndrome SARS-CoV-2 PCR test	X			X	
Temperature check	X	X		X	
Inclusion and exclusion criteria	X				Recheck clinical status before randomization and/or 1st dose of study intervention.
Demography	X				
Full physical examination including height and weight.	X				Weight at screening is used for determination of dose
Fitzpatrick Skin Type	X				Assessments for UVB-MITT population only Assessment to determine applying MED application
Echocardiogram	X				
Medical history (includes substance usage)	X				Substances: Drugs, Alcohol, tobacco and caffeine
Current medical conditions	X				
HIV, Hepatitis B and C	X				
Haematology, clinical chemistry (include liver chemistries) and urinalysis	X			X	Including Troponin-T (hs)
NT-proBNP	X			X	
UrDrug, BrAlc	X			X	
12-lead ECG	T			X	T = Triplicate X = Single
Vital signs	X			X	

Procedure	Screening (up to 28 days before Day 1)		Follow-up check 36 ± 4 days post last dose	Final follow-up 56 ± 4 days post-last dose	Notes
	Part 1	Part 2			
PainCart training	[X]	[X]			May be performed during either part 1 or part 2 (not both)
Minimal Erythema Dose (MED) application		X			Assessments for UVB-MITT population only. Exposure to pre-determined 6 ascending doses of UVB radiation. MED application will be the final assessment on Part 1 of Screening and will only be completed after confirmation of eligibility from available results, e.g. lab data, echocardiogram results may not be available.
MED assessment		X			Assessments for UVB-MITT population only. 24 hours (± 2 hours) after UV exposure
AE/SAE review	X	X	X	X	

- An echocardiogram performed within 3 months prior to first dosing is acceptable for enrolment into the study
- MED determination performed within 6 weeks prior to first dosing is acceptable for enrolment into the study

12.2.1.2. Study periods 1, 2, 3 and Early Withdrawal

When the following assessments are scheduled to be performed at the same time-point, the order will be as follows:

ECG > vital signs > PK and PD sampling > PainCart

Procedure	Study periods 1, 2, 3 (Days)								Early Withdrawal	Notes
	-2	-1	1	2	7	8	15	25		
Out-patient visit					X*	X	X		X	Optional in-clinic stay for participants at the discretion of investigator. *Day 7 is optional for those participants not receiving UVB.
Admission in clinical unit	X**									Optional in-clinic stay for participants at the discretion of investigator. ** If subjects are not UVB-MITT participants, optional admission will be on Day-1 with Day-2 completed on Day-1.
Discharge from clinical unit				X						Except if, the participant needs to remain in the Unit longer for medical reasons.
Phone Call							X			AE collection - may be out-patient visit at discretion of Investigator for additional checks
Brief Physical Examination			X	X		X	X		X	
Haematology, clinical chemistry (include liver chemistries) and urinalysis		X	X	X		X	X		X	Troponin T to be assessed on Day -1, 8, 15 (and EW if needed). C3/C4 on Day -1 only
UrDrug, BrAlc		X			X*		X			*for volunteers who do not receive UVB application, the Day 7 Assessments may be performed on Day 8 prior to PainCart
SARS-CoV-2 PCR test	X**								X	

Procedure	Study periods 1, 2, 3 (Days)								Early Withdrawal	Notes
	-2	-1	1	2	7	8	15	25		
12-lead ECG		T	X			X	X		X	Day 1: pre-dose (T), 0.5hr, 1hr post start of infusion. On other days a single measure taken prior to 1 st PainCart assessment. T = Triplicate X = Single
Vital signs (including temperature)	X**	X	X	X	X-t	X	X		X	Day 1: pre-dose, 0.5hr, 1hr, 2hr post start of infusion. X-t: temperature assessment on Day 7 for UVB-MITT population only On other days a single measure taken prior to 1 st PainCart assessment.
Randomization			X							Study period 1 only
Drug/placebo IV infusion			X							Continuous infusion over 1 hour
PainCart			X	X		X	X			Day 1 pre-dose performed twice (baseline) Day 1 performed at 1 and 3 hours post start of IV infusion. Other days performed twice ~2 hours apart at approximately the same time of day in each study period. Day 15 - heat pain detection assessment associated with UVB test performed on normal skin only. Participants not receiving UVB application will not undergo UVB heat pain detection test on irradiated skin. All other PainCart assessments including heat pain detection performed on normal skin will still be assessed. See Appendix 7 of protocol for details of testing
UVB application		X			X					UVB application (2 x MED) will be performed 24hr (\pm 2hr) prior to start of infusion on Day 1. UVB application (2 x MED) on Day 7 will be performed 24hr (\pm 2hr) prior to PainCart assessment on Day 8. UVB application only applies to those in the UVB-MITT population.

Procedure	Study periods 1, 2, 3 (Days)								Early Withdrawal	Notes
	-2	-1	1	2	7	8	15	25		
AE review	X**	X	<=====→						X	
SAE review	X**	X	<=====→						X	
Concomitant medication review	X**	X	<=====→						X	
Blood samples for PK and PD			X	X		X	X		X	Day 1: pre-dose, 1hr, 3hr post-start of IV infusion. On other days samples taken prior to 1 st PainCart assessment.
Blood sample for immunogenicity			X			X			X	Day 1: pre-dose. Day 15: prior to 1 st PainCart assessment.

** If subjects are not UVB-MITT participants, optional admission will be on Day-1 with Day-2 assessments completed on Day-1.

- The timing and number of planned study assessments, including safety, pharmacokinetic, pharmacodynamic assessments may be altered during the course of the study based on newly available data to ensure appropriate monitoring.
- Any changes in the timing or addition of time points for any planned study assessments as the result of emerging pharmacokinetic/pharmacodynamic data from this study must be documented and approved by the relevant study team member and then archived in the sponsor and site study files but will not constitute a protocol amendment. The Competent Authority (CA) and ethics committee (EC) will be informed of any safety issues that constitute a substantial amendment and require alteration of the safety monitoring scheme or amendment of the informed consent form (ICF). The changes will be approved by the CA and the EC before implementation.
- The planned study assessments on Day 7 (UVB-MITT population only), 8, 15 and 25 may be performed within a ± 24hr window.
- A questionnaire related to COVID-19 is part of each visit and included in the AE review.

12.3. Appendix 3: Assessment Windows

12.3.1. General

Clinic visits are scheduled to take place as specified in [Appendix 2: Schedule of Activities](#). Measurements will be reported based on the visits they are assigned to in the study database without adjustment. Measurements outside visit windows will not be excluded from analyses and may constitute an important protocol deviation upon further review.

If a circumstance should arise where multiple measurements have been collected and recorded against the same scheduled visit and timepoint, for which only one measurement should have been collected, then the first valid value will be used for that timepoint.

12.3.2. PainCart Assessment Window

During each study period, all participants will be assessed on the various PainCart tests for measuring different modalities of nociception. The PainCart assessments are performed multiple times during each study period and taken multiple times during each clinical visit.

The following information in [Table 4: PainCart Assessment Windows](#) displays which PainCart assessments relate to which day, and how they are summarised at each visit. As a note, the AAUC analysis for the PainCart endpoints will utilise the individual assessments instead of the summarised daily assessments detailed below.

Table 4 PainCart Assessment Windows

PainCart Assessment Windows		
Analysis Day	Analysis Period	Summarised
	Timepoint	
Baseline	Day 1 (Randomisation, Pre-Dose)	Two assessments are performed pre-dosing. Baseline is defined as the mean value prior to dosing in each study period. If only one pre-dose assessment record is present on Day 1, then this value will be set as the baseline value
Day 1	Day 1 (Randomisation, Post-Dose)	Two assessments are performed at 1 and 3 hours post start of IV infusion. The analysis day value is defined as the mean value of the two assessments. If only one post-dose assessment is performed on Day 1, then that value will be set as the analysis day value..

PainCart Assessment Windows		
Analysis Day	Analysis Period	
	Timepoint	Summarised
Day 2, 8 and 15	Day 2, 8 and 15 from day of randomisation	
Two assessments are performed at approximately 2 hours apart at roughly the same time of day in each study period. The analysis day value is defined as the mean value of the two assessments. If only one assessment is performed on the day, then that value will be set as the analysis day value.
 
The planned PainCart assessments on day 2, 7 (MED application), 8 & 15 may be performed within a \pm 1-24hr window.

Acceptable time windows around the nominal time points for other assessments will be included in the Study Reference Manual (SRM) and assessments performed within these time windows will not constitute a protocol deviation.

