PainCart			X	X		X	X			Day 1 pre-dose performed twice (baseline) Day 1 performed at 1 and 3 hours post start of IV infusion. Other days performed twice ~2 hours apart at approximately the same time of day in each study period. Day 15 - heat pain detection assessment associated with UVB test performed on normal skin only. Participants not receiving UVB application will not undergo UVB heat pain detection test on irradiated skin. All other paincart assessments including heat pain detection performed on normal skin will still be assessed. See Appendix 7 for details of testing
UVB application		X			X					UVB application (2 x MED) will be performed 24hr (\pm 2hr) prior to start of infusion on Day 1. UVB application (2 x MED) on Day 7 will be performed 24hr (\pm 2hr) prior to PainCart assessment on Day 8. UVB application only applies to those in the UVB-MITT population.

Procedure	Study periods 1, 2, 3 (Days)								Early Withdrawal	Notes
	-2	-1	1	2	7	8	15	25		
AE review	X**	X	<=====→						X	
SAE review	X**	X	<=====→						X	
Concomitant medication review	X**	X	<=====→						X	
Blood samples for PK and PD			X	X		X	X		X	Day 1: pre-dose, 1hr, 3hr post-start of IV infusion. On other days samples taken prior to 1 st PainCart assessment.
Blood sample for immunogenicity			X			X			X	Day 1: pre-dose. Day 15: prior to 1 st PainCart assessment.

** If subjects are not UVB-MITT participants, optional admission will be on Day-1 with Day-2 SARS-CoV-2 test performed on Day-1.

- The timing and number of planned study assessments, including safety, pharmacokinetic, pharmacodynamic assessments may be altered during the course of the study based on newly available data to ensure appropriate monitoring.
- Any changes in the timing or addition of time points for any planned study assessments as the result of emerging pharmacokinetic/pharmacodynamic data from this study must be documented and approved by the relevant study team member and then archived in the sponsor and site study files but will not constitute a protocol amendment. The Competent Authority (CA) and ethics committee (EC) will be informed of any safety issues that constitute a substantial amendment and require alteration of the safety monitoring scheme or amendment of the informed consent form (ICF). The changes will be approved by the CA and the EC before implementation.
- The planned study assessments on Day 7 (UVB-MITT population only), 8, 15 and 25 may be performed within a ± 24hr window.

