10.7.1.1.1. Thermal pain

Thermal pain detection and tolerance thresholds are determined using the Q-sense (Medoc, Israel), which controls a 30 x 30 mm thermode that is placed on the subjects

back. The initial temperature of the thermode will be 32°C and will increase by $0.5^{\circ}\text{C}\cdot\text{s}^{-1}$ until the subject perceives the stimulus as painful (Pain Detection Threshold [PDT] - indicated with pushing a button on a hand-held feedback control) or when a temperature of 50°C is reached. The average of a triplicate measurement will be used to determine pain thresholds.

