7.1.2. Summary Measure

For each of the three endpoints, the Analysis Area Under the Curve (AAUC) of the Ratio to Baseline will be the primary summary measure. The PainCart assessments will be log transformed in order to calculate the log change from baseline result which will be used for the primary analysis, and back transformed to obtain the ratio to baseline result. As default, summaries of Change from Baseline will also be calculated. If modelling assumptions are invalidated, then the results will not be presented. Ratio to baseline and change from baseline will be measured at each day where the assessment was performed. The AAUC is calculated via the trapezoidal method and will be normalised. Further details are referenced in Section 12.6.3 Pharmacodynamic.

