7.1.5.1. Statistical Methodology Specification

7.1.5.1.1. UVB heat pain detection (Celsius)

Endpoint / Variables

 Ratio to baseline (or change from baseline) in UVB heat pain detection (Celsius) AAUC(1-8 Days) If ratio to baseline is deemed suitable due to the distribution of the parameters, the response will be log transformed. Any transformation of a response variable is also expected to be applied to the corresponding baseline variable. Final decisions on transformations will be based on the observed data and model diagnostics
Model Specification

The analysis will be performed on the AAUC (1-8 days) using a Bayesian Mixed Analysis of Covariance (ANCOVA) model.
 
Refer to Section 12.6.3 Pharmacodynamic for the derivation of the AAUC via the trapezoidal method.
 
Non-informative priors will be utilized for each model parameter as either a normal distribution with a mean = 0 and variance = 1e6 (very large variance), unless specified elsewhere.
 
The prior for the variance covariance matrix will follow an inverse Wishart distribution. An inverse Wishart prior on the covariance matrix is chosen as it ensures sampling efficiency with PROC MCMC using the conjugate sampler to draw the unstructured covariance.
 
The random seed to use has been calculated prior to unblinding. Section 12.6 details the seed to use for the analyses in this RAP.
 
The mixed model ANCOVA will be fitted using Bayesian techniques with PROC MCMC using the following approach:
 
 Assume equal variances across treatment arms and use a pooled estimate of residual variability. Fit the following model: 
 M: Intercept + Treatment + Time of Assessment Stratum + Subject Level Baseline + Period Level Baseline + Study Period + Study Period*Period Level Baseline + Treatment*Study Period Time of assessment stratum (AM, PM) may be removed from the model if model convergence issues arise. For the model, use appropriate combinations of the model parameters (back transforming the combination if response variable is ratio to baseline) to obtain posterior distributions for the variables of interest. Binary flag variables can be used to evaluate the probability statements.

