
 The weighted mean AAUC parameters will be derived by calculating the area under the curve (AUC) using the trapezoidal rule, and then dividing by the actual relevant time interval (i.e. $t_f - t_l$): $\textbf{Weighted Mean AAUC}(t_f - t_l) = \frac{\frac{1}{2} \sum_{i=1}^{I-1} (t_{i+1} - t_i)(y_{i+1} + y_i)}{t_l - t_f}$ 
Where (example provided for UVB heat pain detection AUC(1-8 Days):
 
 y_i = Value of endpoint at i^{th} time point t_i = The i^{th} actual time point (days) for UVB heat pain detection: 
 t values will be calculated as the actual time recorded in the SAS dataset in the SAS datetime format. For baseline, the timepoint will be calculated as the midpoint of the two pre-dose assessments. t_f = Actual time point of first non-missing obs t_l = Actual time point of last non-missing obs I = Number of time points used in the AAUC calculation 					
Seeds for PainCart Analyses – PROC MCMC					

 Seeds for all planned analyses were determined in advance using the following SAS code (analysis_seed.SAS) and documented within this RAP prior to unblinding: <pre>data temp; do i = 1 to 15; number=round(100000*ranuni(0),1); output; end; run; proc print; run;</pre>					
Endpoint	Test	Analysis	Macro Seed		
Heat Pain	Detection	Mixed ANCOVA	57743		

PainCart Assessments			
Cold Pressor	Tolerance	Mixed ANCOVA	95933
	Detection	Mixed ANCOVA	55572
Electrical Pain – single stimulus (Pre-cold pressor)	Tolerance	Mixed ANCOVA	01749
	Detection	Mixed ANCOVA	19282
Conditioned Pain Modulation (CPM)	Detection	Mixed ANCOVA	46555
	Tolerance	Mixed ANCOVA	33042
Electrical Pain – repeated stimulus	Tolerance	Mixed ANCOVA	80088
	Detection	Mixed ANCOVA	73186

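### Does building the AAUC from individual readings waste the second reading at the last visit?

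*SAP*

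**What the plan says.** Three primary endpoints are summarised by a time-weighted mean of the log ratio to baseline. The window is Days 1-8 for UVB heat pain and Days 1-15 for cold pressor and electrical tolerance. SAP 7.1.2 says the readings "will be log transformed in order to calculate the log change from baseline result which will be used for the primary analysis".

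The visit schedule in Protocol 1.3.2 places post-dose PainCart sessions at 1 and 3 hours on Day 1; on later days the schedule reads "Other days performed twice ~2 hours apart at approximately the same time of day in each study period". For by-visit summaries the pair is averaged (SAP 12.3.2, Table 4): "The analysis day value is defined as the mean value of the two assessments". For the AAUC it is not: "the AAUC analysis for the PainCart endpoints will utilise the individual assessments instead of the summarised daily assessments detailed below". SAP 12.6.3 then says the AAUC "will be derived by calculating the area under the curve (AUC) using the trapezoidal rule, and then dividing by the actual relevant time interval", using actual times.

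The pre-dose pair is handled differently. Its mean is the baseline value, and "For baseline, the timepoint will be calculated as the midpoint of the two pre-dose assessments".

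**The concern.** A trapezoid weights each reading by half the distance to each neighbour. When two readings sit 2 hours apart at the end of the window, the last one is worth half of 2 hours in a window of 7 or 14 days. The site takes two readings at the last visit, yet the AAUC depends almost wholly on the first. Day 2 is lopsided the other way, because its first reading sits close to Day 1 and its second faces the long gap to Day 8.

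For UVB, two readings (second on Day 2, first on Day 8) carry 84% of the primary measure, although four were taken at those visits. The SAP already pools the pre-dose pair, so leaving the post-dose pairs unpooled looks like avoidable noise. In a study stopped for futility, one would ask whether the summary measure had thrown information away.

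**Working it through.** The plan states no AAUC weight or precision figure, so there is none to reproduce.

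**Inputs.** Nominal hours from infusion start are 1, 3, 24, 26, 168, 170, and for the 15-day window also 336, 338 (Protocol 1.3.2; SAP 12.3.2). The baseline node is put at hour -1; this is an assumption, since no clock time is given. The span is 171 h for UVB and 339 h for the 15-day endpoints.

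**Weights.** Each reading gets (half the gap before + half the gap after) / span.

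| Reading | UVB, Days 1-8 | Days 1-15 |
|---|---|---|
| Day 2 first | (10.5 + 1)/171 = 6.7% | 11.5/339 = 3.4% |
| Day 2 second | (1 + 71)/171 = 42.1% | 72/339 = 21.2% |
| Day 8 first | (71 + 1)/171 = 42.1% | 72/339 = 21.2% |
| Day 8 second | 1/171 = 0.6% | (1 + 83)/339 = 24.8% |
| Day 15 first | none | (83 + 1)/339 = 24.8% |
| Day 15 second | none | 1/339 = 0.3% |

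The Day 8 pair inside the 15-day window is nearly balanced. On Day 2 the first reading has 6.7/48.8 = 14% of its pair's weight. That split is worth 1/(0.14² + 0.86²), or about 1.3 independent readings. Only the last visit is close to a single reading.

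**Daily-mean nodes.** With nodes at -1, 2, 25, 169 (and 337) the day weights barely move: UVB Day 2 goes from 48.8% to 49.1% and Day 8 from 42.7% to 42.4%. Both versions target practically the same time average.

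**Precision.** Let rho be the correlation between two readings on one day, with days independent and reading variance 1. The planned AAUC has variance equal to the sum over days of w1² + w2² + 2·rho·w1·w2. The daily-mean version has the sum of W²(1 + rho)/2. The SE increase is the square root of their ratio, minus 1.

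| rho | UVB variances | UVB SE increase | 15-day variances | 15-day SE increase |
|---|---|---|---|---|
| 0 | 0.364 vs 0.213 | 31% | 0.215 vs 0.169 | 13% |
| 0.5 | 0.395 vs 0.320 | 11% | 0.276 vs 0.253 | 4% |
| 0.9 | 0.421 vs 0.405 | 2% | 0.325 vs 0.320 | 1% |

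These figures suppose that the baseline covariates ("Subject Level Baseline + Period Level Baseline + Study Period") remove all baseline error. If none is removed, (sum of post-baseline weights)²·(1 + rho)/2 is added to both variances. The increases become 10%/4%/1% for UVB and 4%/1%/0.3% for the 15-day endpoints. The truth lies between.

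Real data also vary from period to period within a person, which averaging same-day readings cannot reduce. Suppose this variance equals one reading's variance (assumed). At rho 0 with baseline error removed, UVB gives sqrt(1.364/1.213) - 1 = 6% and the 15-day endpoints sqrt(1.215/1.169) - 1 = 2%.

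**Visit windows.** SAP 2.3 and 12.3.2 also allow Day 2 to move by up to 24 h. I let Day 2 run from 6 h (an assumed lower end) to 48 h and Days 8 and 15 move by ±24 h. At rho 0 with baseline error removed, the UVB increase is about 18% to 39%, and the 15-day increase reaches about 18%. With Day 2 at 48 h, its first reading carries about 28% of the pair's weight (13.7/48.8).

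**UVB triplicates.** Each heat pain value is already a mean (Protocol 10.7.1.1.1): "The average of a triplicate measurement will be used to determine pain thresholds". If single ramps had same-day correlation r with independent ramp errors, the triplicate mean has r/(r + (1 - r)/3). At r = 0.25 this is 0.50, giving 11% for UVB, against 8% for a 15-day endpoint at correlation 0.25. The weights alone therefore do not show that UVB loses most.

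**The case for a change.** The best case for acting is that the weights are certain, the pre-dose pair is already pooled, and a daily-mean AAUC needs no new data. It would take one derivation and one model run per endpoint, could go in the later AAC delivery, and would leave the primary alone. RAP Amendment 1 removed the by-day Bayesian analyses, so no other modelled check on the AAUC remains.

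The weights stand, and the SAP gives no reason for using individual readings. The rest does not lead to a change. The large percentages need independent same-day readings, no period-level variance and fully removed baseline error, all at once. At the last visit alone, even those conditions give only about 15% (UVB) and 8% (15-day); the remainder comes mainly from Day 2. A supplementary model specified after unblinded interim review could only be supportive. It would also add to a package that the sponsor cut on purpose, citing few subjects relative to parameters for the analyses removed. Both readings already feed the visit summaries (Tables 2.01, 2.04 and 2.08), and Listing 32 lists the assessments.

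**Conclusion.** The imbalance is real, but it is a property of a clearly stated time-weighted mean and not an error. It does not bias the treatment comparison. The possible cost in standard error runs from well under 1% to 31% (UVB) or 13% (15-day) at nominal times. It reaches about 39% and 18% in the extreme window scenarios, and is at most about 6% and 2% at nominal times once period-level variance equal to one reading's is assumed. All of this rests on assumed correlations, because the documents give no within-day variance.

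For scale, if a given effect has 80% power under the plan, removing a 5% SE inflation would raise that to about 83% (normal approximation, one-sided 10%).

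Under Protocol 9.5 the futility decision turned on cold pressor and electrical tolerance, and it had been taken before RAP Amendment 1. Its criteria are in an interim charter that is not among these documents, so the effect on that decision cannot be assessed. A daily-mean AAUC is an optional display. It would change neither the primary result nor the stopping decision, so the plan can stay as written.
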